4.2.6 Subpopulations

The subgroups of interest for this study are the following:

- Intrinsic factors
 - Age: categorized as < 40, \geq 40, < 65, \geq 65
 - Sex: female, male
 - Sex and age: female < 40, female \geq 40, male < 40, male \geq 40
 - Race: white, black or African American, other including Asian, Asian
 - Ethnicity: Hispanic or Latino, not Hispanic or Latino
- Extrinsic disease-related factors
 - CV risk contraindicating triptans: yes, no (see Section 5.2.2)
 - Baseline body mass index (BMI; kg/m²): categorized as < 25, \geq 25 to < 30, \geq 30
 - Prophylactic migraine medication use on or after study drug start: yes, no (see Section 4.9)
- Extrinsic exposure factors
 - Time on rimegepant (weeks): categorized as quintiles for treated subjects (see Sections 4.8.1 and 5.2.3)

- Cumulative rimegepant exposure (tablets): categorized as quintiles for treated subjects (see Sections 4.8.1 and 5.2.3)
- Key factors
 - Average rimegepant exposure (tablets per 4 weeks): categorized as < 2, ≥ 2 to < 8, ≥ 8 to < 14, ≥ 14 for treated subjects (see Section 4.8.1)
 - Average rimegepant exposure (tablets per 4 weeks) for EOD+PRN treated subjects: categorized as < 14, ≥ 14 (see Section 4.8.1)
 - Treated subjects who took ≥ 14 tablets per 4 weeks for ≥ 12 weeks: categorized by enrollment group (see Section 4.8.1)
 - Treated subjects who took ≥ 20 tablets per 4 weeks for ≥ 4 weeks: categorized by enrollment group (see Section 4.8.1)
 - Treated subjects with near-daily dosing, defined as those in the (1) PRN dosing groups who took ≥ 14 tablets per 4 weeks for ≥ 12 weeks (see previous bullet), or (2) EOD+PRN dosing group: categorized by enrollment group.

Subgroup levels may be combined or redefined based on the availability of the data.

Subgroup tabulations will be by subgroup level and overall for treated subjects with non-missing subgroup level data. Refer to the BHV3000 Core SAP for rounding rules.

The triptan non-responder (yes, no) subgroup will be derived according to Section 5.2.1, included in the subgroup summary table (see Section 4.5), and excluded from subgroup tabulations by subgroup level and overall.

4.2.7 *Withdrawals, Dropout and Loss to Follow-Up*

Subjects who withdrew from the study were not replaced.

4.2.8 *Missing, Unused and Spurious Data*

Analyses will be based on observed data only.

4.3 *Planned Analyses*

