4.6.3 Exploratory Safety and Other Endpoints

4.6.3.1 LFT Elevations

The number and percentage of subjects with LFT elevations will be summarized separately for the following populations and safety analysis periods:

- Screened subjects during pre-treatment by enrollment group, and overall
- Treated subjects during pre-treatment by enrollment group and overall
- Treated subjects on-treatment by enrollment group and overall
- Treated subjects on-treatment by subgroup level and overall for all subgroups of interest specified in Section 4.2.6
- Treated subjects on-treatment by enrollment group and overall for subjects who did not participate in previous Studies BHV3000-301/302/303
- Follow-up subjects during follow-up by enrollment group and overall.

LFT elevations include the following endpoints:

- Cumulative elevations:
 - ALT $> 1 \times, > 3 \times, > 5 \times, > 10 \times$, and $> 20 \times$ ULN
 - AST $> 1 \times, > 3 \times, > 5 \times, > 10 \times$, and $> 20 \times$ ULN
 - ALT or AST $> 1 \times, > 3 \times, > 5 \times, > 10 \times$, and $> 20 \times$ ULN
 - TBL $> 1 \times, 1.5 \times$, and $> 2 \times$ ULN
 - Alkaline phosphatase (ALP) $> 1 \times, > 1.5 \times$, and $> 2 \times$ ULN

- Mutually exclusive elevations:
 - ALT > ULN to $\leq 3 \times$ ULN, $> 3 \times$ ULN to $\leq 5 \times$ ULN, $> 5 \times$ ULN to $\leq 10 \times$ ULN, $> 10 \times$ ULN to $\leq 20 \times$ ULN, and $> 20 \times$ ULN
 - AST > ULN to $\leq 3 \times$ ULN, $> 3 \times$ ULN to $\leq 5 \times$ ULN, $> 5 \times$ ULN to $\leq 10 \times$ ULN, $> 10 \times$ ULN to $\leq 20 \times$ ULN, and $> 20 \times$ ULN
 - ALT or AST > ULN to $\leq 3 \times$ ULN, $> 3 \times$ ULN to $\leq 5 \times$ ULN, $> 5 \times$ ULN to $\leq 10 \times$ ULN, $> 10 \times$ ULN to $\leq 20 \times$ ULN, and $> 20 \times$ ULN
- Composite elevations:
 - ALT or AST $> 3 \times$ ULN and TBL $> 1.5 \times$ ULN
 - ALT or AST $> 3 \times$ ULN and TBL $> 2 \times$ ULN
 - ALT or ALT $> 3 \times$ ULN concurrent with TBL $> 2 \times$ ULN with Agresti-Coull 95% CIs (see Section 4.6.2)
 - ALT or ALT $> 3 \times$ ULN concurrent with TBL $> 2 \times$ ULN and ALP $\leq 2 \times$ ULN with Agresti-Coull 95% CIs (see Section 4.6.2)
 - ALT or AST $> 3 \times$ ULN concurrent with AEs of interest (nausea, vomiting, anorexia, abdominal pain, fatigue; see Section 4.6.3.2).

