Exposure-adjusted on-treatment cumulative LFT elevations will also be summarized for treated subjects with the number and percentage of subjects with LFT elevations, along with patient-years and exposure-adjusted rates based on exposure up to time of first LFT elevation (see Section 4.8.2).

By-subject longitudinal LFT plots will display all normalized results (i.e., LFT ratio of value to ULN) regardless of study period for AST, ALT, ALP and TBL on the y-axis versus study week of laboratory result on the x-axis for treated subjects with any of the following LFT elevations during a safety analysis period (pre-treatment, on-treatment, follow-up): ALT $> 3 \times$ ULN; AST $> 3 \times$ ULN; TBL $> 2 \times$ ULN; ALP $> 2 \times$ ULN. Study week is defined as study day/7 (see Section 5.5). Each figure will also display treated migraine onsets, start of the on-treatment safety analysis period, and start of the follow-up safety analysis period.

Additionally, an evaluation of Drug-Induced Serious Hepatotoxicity (eDISH) scatter plot will display the maximum TBL ratio of value to ULN on the y-axis versus the maximum ALT ratio of value to ULN on the x-axis, where the maxima will be in the same safety analysis period but not necessarily concurrent. Both axes will be on the \log_{10} scale. Ratios $< 0.1 \times$ ULN will be set to 0.1. Sample sizes in the legend will represent subjects with paired ratios. A horizontal reference line will be placed at $2 \times$ ULN, and a vertical reference line will be placed at $3 \times$ ULN. The lower left quadrant will be labeled “Normal Range”, the upper left quadrant will be labeled “Hyperbilirubinemia”, the lower right quadrant will be labeled “Temple’s Corollary”, and the upper right quadrant will be labeled “Possible Hy’s Law Range.” The following eDISH scatter plots will be produced for treated subjects: (1) on-treatment by enrollment group; (2) on-treatment by average rimegepant exposure; (3) on-treatment by average rimegepant exposure for the EOD+PRN dosing group; (4) on-treatment by enrollment group for treated subjects who

took ≥ 14 tablets per 4 weeks for ≥ 12 weeks; (5) by safety analysis period (pre-treatment, on-treatment, follow-up) across enrollment groups pooled; (6) on-treatment by enrollment group for treated subjects who took ≥ 20 tablets per 4 weeks for ≥ 4 weeks; (7) on-treatment by enrollment group for treated subjects with near-daily dosing.

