 - ≥ 14 tablets per 4 weeks for 4, 8, 12, 16, 20, ≥ 24 , ≥ 12 , and ≥ 4 weeks (the “ ≥ 12 weeks” category will support the subgroup “treated subjects who took ≥ 14 tablets per 4 weeks for ≥ 12 weeks” specified in Section 4.2.6)
 - ≥ 20 tablets per 4 weeks for 4, 8, 12, 16, 20, ≥ 24 , ≥ 12 , and ≥ 4 weeks
 - ≥ 25 tablets per 4 weeks for 4, 8, 12, 16, 20, ≥ 24 , ≥ 12 , and ≥ 4 weeks
- Total rimegepant exposure (tablets) summed across all subjects, derived by summing cumulative exposure across all subjects
- Total rimegepant exposure (patient-years), derived by summing (study drug end dose date – study drug first dose date + 1)/365.25 across all subjects.

This summary will also display quintiles (e.g., P20, P40, P60, P80, where “PX” denotes Xth percentile) for asterisked (“*”) continuous parameters to support the derivation of rimegepant exposure subgroups (see below). See Section 5.3 for derived dates.

eDiary exposure over time will assess the number of 4-week (28-day) intervals in which a subject exceeded select tablet counts in the LTT analysis period (see Section 5.4), where the number of 4-week intervals are not necessarily consecutive. For example, suppose a subject takes 20 tablets through 4 weeks (interval 1; LTT study days 1 to 28), 10 tablets after 4 weeks to 8 weeks (interval 2; LTT study days 29 to 56), 25 tablets after 8 weeks to 12 weeks (interval 3; LTT study days 57 to 84), and 15 tablets after 12 weeks to 16 weeks (interval 4; LTT study days 85 to 112). Thus, this subject is considered to have taken ≥ 14 tablets per 4 weeks for 12 weeks (i.e., intervals 1, 3 and 4), ≥ 20 tablets per 4 weeks for 8 weeks (i.e., intervals 1 and 3), and ≥ 25 tablets per 4 weeks for 4 weeks (i.e., interval 3). See Section 5.5 for the definition of LTT study days.

eDiary exposure will also be summarized by subgroup level and overall for treated subjects for all subgroups of interest described in Section 4.2.6.

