4.8.2 Adverse Events

Refer to the BHV3000 Core SAP for AE start date imputation, AE counting rules, definition of treatment-emergent adverse events (TEAEs), and definition of AEs related to study drug.

Tables will present the number and percentage of subjects experiencing AEs by SOC and PT, unless specified otherwise.

A by-subject listing of all AEs will be provided for screened subjects that will flag on-treatment and treatment-emergent AEs. Additional by-subject listings of deaths, SAEs, AEs leading to study drug discontinuation, hepatic-related AEs, and AEs of special interest (i.e., potential drug abuse, CV, and suicidality) will be provided for screened subjects. Refer to the BHV3000 Core SAP for listing content and AEs of special interest.

AE Overview

An AE overview without SOC and PT will present the number and percentage of subjects with any the following AEs: any AE; severe AE; AE related to study drug (unlikely related, possibly related, or related); SAE; SAE related to study drug; AE leading to study drug discontinuation; AE leading to death; hepatic-related AE; severe hepatic-related AE; hepatic-related SAE; hepatic-related AE leading to study drug discontinuation; potential drug abuse AE; CV AE; suicidality AE. An AE overview will be produced for each the following analysis periods and populations:

- Pre-treatment AEs for screened subjects by enrollment group and overall
- Pre-treatment AEs for treated subjects by enrollment group and overall
- TEAEs for treated subjects by enrollment group and overall
- On-treatment AEs for treated subjects by enrollment group and overall
- On-treatment AEs for treated subjects by subgroup level and overall for all subgroups of interest specified in Section 4.2.6
- Follow-up AEs for follow-up subjects by enrollment group and overall.

Pre-Treatment AEs

Pre-treatment AEs will be summarized by SOC and PT by enrollment group and overall for screened subjects for the following endpoints:

- AEs
- SAEs.

Pre-treatment AEs will be summarized by SOC and PT for treated subjects by enrollment group and overall for the following endpoints:

- AEs by severity (total, mild, moderate, severe, moderate or severe, not reported)
- SAEs.

On-Treatment AEs

On-treatment AEs will be summarized by SOC and PT for treated subjects by enrollment group and overall for the following endpoints:

- AEs by severity*
- TEAEs by severity

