- TEAEs occurring in $\geq 2\%$ of subjects in any enrollment group after rounding. Percentages will be displayed rounded to integers, and AEs will be displayed in alphabetical order by SOC and PT.
- AEs occurring in $\geq 2\%$ of subjects in any enrollment group or subgroup level[^]
- AEs occurring in $\geq 5\%$ of subjects in any enrollment group by severity (primary safety endpoint, see Section 4.6.1)
- AEs occurring in $\geq 10\%$ of subjects in any enrollment group
- Exposure-adjusted AEs
- AEs related to study drug by severity*
- AEs related to study drug occurring in $\geq 2\%$ of subjects in any enrollment group or subgroup level[^]
- SAEs (primary safety endpoint, see Section 4.6.1)*
- Exposure-adjusted SAEs
- AEs leading to study drug discontinuation (primary safety endpoint, see Section 4.6.1)*
- Hepatic-related AEs by severity (secondary safety endpoint, see Section 4.6.2)[#]
- Hepatic-related SAEs[#]
- Hepatic-related AEs leading to study drug discontinuation (secondary safety endpoint, see Section 4.6.2)[#]
- Additional AEs of special interest: potential drug abuse[^]; CV; suicidality. Potential drug abuse AEs will be displayed in alphabetical order by severity and PT without SOC.

Endpoints marked with “*” will also be summarized by subgroup level and overall for all subgroups of interest specified in Section 4.2.6. Endpoints marked with “#” will also be summarized by subgroup level and overall only for extrinsic exposure factors (see Section 4.2.6). Endpoints marked with “^” will also be summarized by subgroup level and overall only for key extrinsic exposure factors (see Section 4.2.6).

Refer to the BHV3000 Core SAP for exposure-adjusted AEs. Calculations for on-treatment exposure-adjusted AEs will set reference start date to the study drug first dose date, reference end date to the study drug end dose date, and reference last date to the study drug last dose date + 7 days.

Follow-up AEs

Follow-up AEs will be summarized by SOC and PT for follow-up subjects by enrollment group and overall for the following endpoints:

- AEs by severity
- SAEs.

AEs in All Safety Analysis Periods Combined

AEs in all safety analysis periods combined (i.e., pre-treatment, on-treatment, and follow-up) will be summarized by SOC and PT for treated subjects by enrollment group and overall for the following endpoints:

- AEs leading to study drug discontinuation (primary safety endpoint, see Section 4.6.1)

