5.4 Analysis Periods

Analysis periods are defined as follows:

- Observational Period (OP): measurement date/time on or after the OP start date/time through the OP end date/time. This period is used to assess the number of migraine days per 4 weeks during the OP.
- Pre-treatment: measurement date/time on or before the study drug first dose date/time. This period is used to derive baseline values, and to assess safety and outcomes research endpoints.
- Post-enrollment: measurement date/time after the IWRS enrollment date/time through the EOT visit date + 7 days. This period is used to derive analysis visit windows for slotting observations.
- Follow-up: measurement date after the EOT visit date + 7 days. This period is used to slot observations.
- Long-term treatment (LTT): measurement date/time on or after the LTT start date/time through the LTT end date/time. This period is used to assess the number of migraine days per 4 weeks and number of tablets taken during LTT.
- On-treatment safety: measurement date/time after the study drug first dose date/time through the study drug last dose date + 7 days. Note that AEs with imputed start date equal to the study drug first dose date are part of this period (refer to the BHV3000 Core SAP for AE start date imputation). This period is used to assess safety endpoints on treatment.
- Follow-up safety: measurement date after the study drug last dose date + 7 days. This period is used to assess safety endpoints during follow-up.

See Section 5.3 for derived dates for determining analysis periods. If measurement time is missing or not collected, then the measurement date will be compared to the derived date.

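### Subgroups defined by reaching a tablet threshold at any time in treatment count adverse events and peak liver tests from the whole on-treatment period, including time before the threshold was reached

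*SAP*

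**What the plan says.** **Who enters.** SAP 4.2.6 names as key factors "Treated subjects who took ≥ 20 tablets per 4 weeks for ≥ 4 weeks: categorized by enrollment group" (the *20-tablet subgroup*) and a subgroup reaching at least 14 tablets per 4 weeks for at least 12 weeks (the *14-tablet subgroup*). Near-daily dosing combines PRN subjects who meet the 14-tablet rule with the whole EOD+PRN group. SAP 4.8.1 counts 28-day intervals in the LTT period, "where the number of 4-week intervals are not necessarily consecutive". One interval therefore suffices for the 20-tablet subgroup and three for the 14-tablet subgroup, in any position.

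**What is counted.** SAP 5.4 defines the on-treatment safety period as "measurement date/time after the study drug first dose date/time through the study drug last dose date + 7 days", whenever the subject qualified. That period feeds:
- the AE overview (SAP 4.8.2): "On-treatment AEs for treated subjects by subgroup level and overall for all subgroups of interest specified in Section 4.2.6";
- AEs by severity, related AEs, SAEs and AEs leading to discontinuation, which "will also be summarized by subgroup level and overall for all subgroups of interest specified in Section 4.2.6" (SAP 4.8.2);
- LFT elevations (SAP 4.6.3.1): "Treated subjects on-treatment by subgroup level and overall for all subgroups of interest specified in Section 4.2.6";
- the eDISH plots, where "the maxima will be in the same safety analysis period but not necessarily concurrent" (SAP 4.6.3.1). Plots 4, 6 and 7 show the 14-tablet, 20-tablet and near-daily subgroups.

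Nothing in the SAP ties an event or liver value to the date of the qualifying interval.

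**The concern.** Membership depends on something that may happen late in treatment, but events are counted from the first dose. Take a subject with ALT above 3 × ULN at Week 8 who first takes 20 tablets in Weeks 37–40. That subject is counted in the 20-tablet LFT table and plotted in eDISH plot 6, although the elevation came months before the high use. The point concerns the order of event and exposure. It does not concern who is in or out of the subgroup.

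The protocol names change in liver tests as the main adverse event of interest (1.3.4), and the contribution of exposure to liver abnormalities is an exploratory objective. Readers will take these outputs as describing safety at high use. Earlier events add cases that do not belong to that use. If there is a true dose effect, earlier lower-use time dilutes it.

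**Working it through.** **1. The SAP's own example.** SAP 4.8.1 gives a subject taking 20, 10, 25 and 15 tablets in intervals 1 to 4. Counting intervals at or above each threshold, times 4 weeks:
- at least 14: intervals 1, 3, 4 → 12 weeks;
- at least 20: intervals 1, 3 → 8 weeks;
- at least 25: interval 3 → 4 weeks.

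All three match the SAP. At the 25-tablet level this subject qualifies on LTT days 57–84 alone, so days 1–56 come first.

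**2. Inputs.** PRN groups dose for up to 52 weeks (K = 13 intervals) and the EOD+PRN group for up to 12 weeks (K = 3) (protocol 7.2.2). The window ends 7 days after last dose (SAP 5.4). Assumption: a completer whose first dose is on LTT day 1 and last dose on the final day. The window is then W = 28K + 7 days, that is 371 days (52 weeks) or 91 days (12 weeks).

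**3. Share of the window before the first qualifying interval k:** 28(k − 1)/W.

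| First qualifying interval (52 weeks) | Days before | Share before | Share kept if counted from its start |
|---|---|---|---|
| 1 | 0 | 0% | 100% |
| 4 | 84 | 22.6% | 77.4% |
| 7 | 168 | 45.3% | 54.7% |
| 10 | 252 | 67.9% | 32.1% |
| 13 | 336 | 90.6% | 9.4% |

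One interval is itself 28/371 = 7.5% of the window. The Weeks 37–40 example is interval 10. For a 12-week subject in the 20-tablet subgroup, the share is 0%, 28/91 = 30.8% or 56/91 = 61.5%.

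**4. Mean share if m qualifying intervals fall at random.** The first lies on average at position (K + 1)/(m + 1), so the mean share is 28[(K + 1)/(m + 1) − 1]/W. For K = 13:
- m = 1: 28 × 6/371 = 45.3%;
- m = 2: 28 × 3.667/371 = 27.7%;
- m = 3: 28 × 2.5/371 = 18.9%;
- m = 6: 28 × 1/371 = 7.5%.

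**5. The 14-tablet subgroup.** It needs at least three intervals, so the random-placement mean for a 52-week subject is at most about 19%. For a single subject the first qualifying interval can be no later than interval 11, giving 280/371 = 75.5%. A 12-week subject has only three full intervals and must qualify in all of them, so interval 1 qualifies and nothing precedes it.

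**6. Near-daily dosing.** EOD+PRN membership is set at screening (SAP 2.2, 4.2.1), so that part has no ordering problem. Only its 52-week PRN subjects are affected.

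**7. Scheduled liver draws.** A 52-week subject has 14 (Weeks 2, 4, 8, …, 52). With one randomly placed interval, the mean share of draws before it depends on where the Week 4 draw falls:
- SAP target days (28, 56, …) put it in interval 1: 90/(13 × 14) = 49%; for 12 weeks, 5/12 = 42%.
- Protocol Table 1 puts it on Day 29, the first day of interval 2: 6/14 = 43%; for 12 weeks, 3/12 = 25%.

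These are shares of draws, not of elevations or of maxima.

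**The case against.** The other side has several good points.

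- **The tables are descriptive.** The label can be read as *subjects who ever reached the threshold*, and the SAP makes no causal claim. That stands, but the SAP does not state that reading, and an exposure-labelled liver plot invites the other one.
- **Single cases can be checked.** Treated subjects with marked LFT elevations get a longitudinal plot showing treated migraine onsets (SAP 4.6.3.1), a listing gives tablets per 4-week interval (SAP 4.8.1), and time to first ALT or AST elevation is tabulated. This helps with individual liver cases but leaves the subgroup tables and eDISH plots unchanged.
- **These are not the plan's only evidence on frequent use.** The EOD+PRN group, the average-exposure subgroups and eDISH plots 2 and 3 also address it. That stands and limits the stakes.
- **Earlier time is not unexposed time.** It follows the first dose and may hold 15 to 19 tablets per interval. That stands: it is time below the threshold.
- **Counting from qualification is also imperfect.** It keeps any lower-use time after the interval, and the interval starts up to four weeks before the 20th tablet. That stands, and it argues for adding a version rather than replacing the present one.

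A reader might infer that the high-exposure tables are inflated, or that about half of their events are misplaced. The documents support neither. They give no event counts and no timing of high-use intervals, and the figures near one half hold only for a single, randomly placed interval. Direction is also open. Earlier events are added, but a subject who stops early has fewer chances to qualify, and an event that ends dosing cannot precede later high use. For AEs leading to discontinuation, the main effect is guaranteed event-free time, which lowers the proportion.

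**Conclusion.** The point holds as a timing misclassification of limited scope. It affects the 20-tablet subgroup in all enrollment groups and, less strongly, the 52-week PRN subjects in the 14-tablet subgroup, and through them the PRN part of near-daily dosing. The outputs concerned are the subgroup AE and LFT tables and eDISH plots 4, 6 and 7. The 12-week subjects in the 14-tablet subgroup and the EOD+PRN part of near-daily dosing are not affected, nor are the tables by enrollment group and overall for all treated subjects.

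The size is unknown. It is nil if every member qualifies in interval 1. The calculated shares rest on completers dosing from LTT day 1, and the means also on random placement, which the documents neither support nor contradict. The documents do not show that the present outputs overstate or understate risk. They do show that the outputs mix time before and after the labelled exposure, and a cheap addition would separate the two.

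**What to change.** 1. Keep the whole-period outputs and label them *subjects who ever reached the threshold*.
2. Derive one date per subject and threshold: the first day of the first qualifying 4-week interval, from the diary intervals SAP 4.8.1 already computes.
3. For the threshold-defined subgroups, add a version of the AE overview, SAE and LFT-elevation tables counting from that date to the end of the on-treatment safety period. Preferably split events into those during qualifying intervals and those after.
4. Give patient-years from the same date in those tables. The exposure-adjusted AE, SAE and LFT tables are not planned by these subgroups, so this is a new line, not a change to an existing rate.
5. In eDISH plots 4, 6 and 7 (PRN subjects only in plot 7), use a different symbol when a plotted maximum precedes that date.

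The cost is SAP wording, one derived date and a few extra tables, with no new data and no protocol change. The restricted version will hold fewer events and less patient-time. Unless it is split, it still includes lower-use time after the qualifying interval.
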